2.4.5.6 Analyses of electrocardiogram variables

- Shift tables will be provided to present ECG status according to baseline status (Normal/Missing, Abnormal) for each treatment group during the 26-week on-treatment period and for FRC group during the on-treatment period of the whole study. Supportive listings of patients with abnormal ECG status at any post-baseline visit will be provided.

2.4.5.7 Analyses of anti-drug antibody variables

Analyses of antibody variables will be performed on the safety population (only in patients from the FRC group).

The number and percentage of patients by antibody status will be listed and summarized by visit, as well as the percentage of conversion from negative to positive status from baseline to Week 26 and Week 52. For anti-insulin glargine antibodies, the number and percentage of patients with cross-reactivity to human insulin will also be summarized by visit in anti-insulin glargine positive patients. For anti-lixisenatide antibodies, the number and percentage of patients with cross-reactivity to GLP-1 and glucagon will be summarized by visit in anti-lixisenatide antibody positive patients.

Antibody levels (titer or concentration), as well as respective percentage changes from baseline for anti-insulin glargine antibodies, will be listed and summarized by visit using descriptive statistics by N, geometric mean, coefficient of variation, median, minimum and maximum.

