7.2.1 Exclusion criteria related to study methodology

- E 01. At screening visit, age under legal age of adulthood;
- E 02. At screening visit, HbA1c <7% (53 mmol/mol) and >9% (75 mmol/mol);
- E 03. At screening visit, Body Mass Index (BMI) ≤ 20 or >40 kg/m²;
- E 04. History of hypoglycemia unawareness;
- E 05. History of metabolic acidosis, including diabetic ketoacidosis within 1 year prior to screening visit;
- E 06. Any use of anti-diabetic drugs within 3 months prior to screening visit (V1) other than those described in I 02;
- E 07. Previous treatment with insulin in the year prior to screening visit (V1) (note: short term treatment with insulin (≤ 10 days) due to intercurrent illness including gestational diabetes is allowed at the discretion of the study physician);
- E 08. Use of systemic glucocorticoids (excluding topical and inhaled forms) for a total duration of 10 days or more within 3 months prior to screening visit;
- E 09. Use of weight loss drugs within 3 months prior to screening visit; or any history of bariatric surgery;
- E 10. Use of any investigational drug within 1 month or 5 half-lives, whichever is longer, prior to screening visit;
- E 11. Personal or immediate family history of medullary thyroid cancer (MTC) or genetic conditions that predispose to MTC (eg, multiple endocrine neoplasia type 2 syndromes);
- E 12. Within the last 6 months prior to screening visit: history of stroke, myocardial infarction, unstable angina, or heart failure requiring hospitalization;
- E 13. Planned coronary, carotid or peripheral artery revascularization procedures to be performed during the study period;
- E 14. Known history of drug or alcohol abuse within 6 months prior to the time of screening visit;
- E 15. Uncontrolled or inadequately controlled hypertension (systolic blood pressure >180 mmHg or diastolic blood pressure >95 mmHg) at screening visit (V1);

E 16. Conditions/situations such as:

- Patients with conditions/concomitant diseases making them non evaluable for the primary efficacy endpoint (eg, hemoglobinopathy or hemolytic anemia, receipt of blood or plasma products within the last 3 months prior to the screening visit);

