11.4.6.6 Analyses of anti-drug antibody variables

Analyses of antibody variables will be performed on the safety population (only in patients from the FRC group).

The number and percentage of patients by antibody status will be listed and summarized by visit, as well as the percentage of conversion from negative to positive status from baseline to Week 26 and Week 52. For anti-insulin antibodies, the number and percentage of patients with cross-reactivity to human insulin will also be summarized by visit in anti-insulin glargine positive patients. For anti-lixisenatide antibodies, the number and percentage of patients with cross-reactivity to GLP-1 and glucagon will be summarized by visit in anti-lixisenatide antibody positive patients.

Antibody levels (titer or concentration), as well as respective percentage changes from baseline for anti-insulin antibodies, will be listed and summarized by visit using descriptive statistics by N, geometric mean, coefficient of variation, median, minimum and maximum.

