2.1.4.8 Immunogenicity variables

Antibody variables in FRC group:

- Anti-insulin glargine antibody:
 - Status (Positive, Negative) and titer;
 - Cross-reactivity of anti-insulin glargine antibodies with human insulin.
- Anti-lixisenatide antibody:
 - Status (Positive, Negative) and concentration;

- Cross-reactivity of anti-lixisenatide antibodies with GLP-1 and glucagon as well as neutralizing effects of these antibodies against lixisenatide, GLP-1 and glucagon.

The on-treatment period for antibody variables is defined as the time from the first injection of open-label IMP up to 28 days after the last injection of open-label IMP.

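### The geometric mean planned for percentage change in anti-insulin antibody titer cannot be validly computed once any titer falls or is unchanged

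*SAP*

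**What the plan says.** SAP Section 2.4.5.7 covers antibody analyses in FRC patients of the safety population. One sentence handles both the level and its change; for the change it says that "percentage changes from baseline for anti-insulin glargine antibodies, will be listed and summarized by visit using descriptive statistics by N, geometric mean". It closes with a single list of statistics for both: "descriptive statistics by N, geometric mean, coefficient of variation, median, minimum and maximum". Protocol Section 11.4.6.6 gives the same instruction, "as well as respective percentage changes from baseline for anti-insulin antibodies, will be listed and summarized by visit", with the same list. The percentage change is planned for the anti-insulin antibody only.

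SAP Section 2.1.4.8 defines the anti-insulin glargine data as "Status (Positive, Negative) and titer" (plus cross-reactivity) and gives no numeric titer to a negative sample. Section 2.4.5.7 also plans "the percentage of conversion from negative to positive status from baseline to Week 26 and Week 52", so patients who are negative at baseline are expected. Under SAP Section 2.5.3 a derived variable is missing when any of its components is missing. SAP Section 2.5.7, the place for technical statistical issues, has no entry.

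**The concern.** The statistic does not fit the variable. Percentage change runs from -100% upward and passes through zero, while a geometric mean is defined only for positive numbers. The rule can therefore be carried out only if every baseline-positive patient's titer rises. Neither document substitutes a ratio to baseline, adds a constant or restricts the set of patients, so the programmer has to improvise.

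There is a second gap. A patient with no titer at baseline has nothing to divide by and so has no percentage change. The text does not say that the change summary is in effect limited to patients already positive at baseline.

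Development of anti-insulin antibodies is a stated objective (Protocol Section 5.3, SAP Section 1.2.3), and samples are scheduled at baseline, Week 26 and Week 52 (Protocol Section 9.2.2.6). This is the planned summary of within-patient change in titer, so it should be computable as specified.

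**Working it through.** The plan states no figure here, so there is nothing to reproduce. The check is whether the stated statistic exists for the stated variable.

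Formulas:
- Percentage change = 100 × (later titer / baseline titer - 1).
- Geometric mean = exp(mean of ln x), which requires every x > 0.
- Ratio to baseline = later titer / baseline titer, which is positive whenever both titers are.

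The documents contain no titers. The values below are assumed, on a two-fold dilution scale.

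| Baseline | Later | % change | ln(% change) | Ratio |
|---|---|---|---|---|
| 8 | 32 | +300 | 5.70 | 4 |
| 8 | 16 | +100 | 4.61 | 2 |
| 16 | 32 | +100 | 4.61 | 2 |
| 4 | 4 | 0 | minus infinity | 1 |
| 8 | 4 | -50 | undefined | 0.5 |
| 16 | 4 | -75 | undefined | 0.25 |
| negative | 8 | none | none | none |
| negative | 16 | none | none | none |

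Results for the six baseline-positive patients:
- Geometric mean of percentage change, all six: not computable. Leaving out the two falls but keeping the tie, the product form gives 0, because one zero makes the whole product zero.
- Geometric mean of percentage change, rises only: (300 × 100 × 100)^(1/3) = 144.2%, N = 3.
- Median (0 + 100)/2 = 50%, minimum -75%, maximum +300%, N = 6. All are well defined.
- Geometric mean ratio: (4 × 2 × 2 × 1 × 0.5 × 0.25)^(1/6) = 2^(1/6) = 1.122, that is 100 × (1.122 - 1) = +12.2%, N = 6.

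A case with no true change: assume log2 ratios of -2, -1, 0, 1 and 2 with probabilities 0.1, 0.2, 0.4, 0.2 and 0.1.
- The share with a positive percentage change is 0.2 + 0.1 = 30%.
- Two thirds of these are +100% and one third +300%, so their geometric mean is 100^(2/3) × 300^(1/3) = 144%.
- The geometric mean ratio is 2^0 = 1 (0% change), and the median change is 0%.

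Coefficient of variation: the plan does not say which form. A geometric CV needs the same logarithms and fails in the same way. An arithmetic CV (SD / mean) can be computed but loses meaning when the mean change is near or below zero.

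Baseline-negative patients: with no titer at baseline, Section 2.5.3 makes the change missing. If negatives were coded at an assumed floor of 2, the last two rows would give +300% and +700%. This part therefore depends on a coding rule that the documents do not give.

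**The case against.** The strongest reply is that this is a wording slip confined to one or two statistics in a row. Most of that reply stands.

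- A reader might infer that only rises can enter the summary. That is true of the geometric mean and a geometric CV, but not of the row: the median and range include falls and ties, and the median in the no-change case correctly reads 0%.
- A reader might infer that the table will be biased upward. Neither document tells anyone to drop non-positive values. Taken literally, the geometric mean is simply not computable, and that would show up at programming. The overstatement arises only if someone then keeps the rises alone.
- A reader might infer that newly positive patients are lost. They lack a percentage change, but their titers are listed and summarised by visit, and status conversion is tabulated.
- A reader might infer from exclusion E 07 (no insulin in the year before screening, short courses allowed) that nearly all FRC patients have no usable value. The documents give no baseline-positive share. If it were 5% to 20%, then 80% to 95% would have none, but that rests on an assumed share and on negatives having no numeric titer.

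It is also fair that no antibody subgroup analysis in the SAP uses change in anti-insulin titer, and that Protocol Section 11.4.5 places immunogenicity results outside the main study report. None of this makes the prescribed geometric mean computable, and nothing elsewhere in the documents repairs it.

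**Conclusion.** The rule is wrong as written, with minor impact. Both documents prescribe a geometric mean, and a coefficient of variation, for a variable that takes zero and negative values. The failure of the geometric mean follows from its definition and needs no assumption beyond at least one baseline-positive patient whose titer falls or is unchanged. The sizes shown (144% against 12%, and 144% against 0%) come from assumed titers and describe only what would happen if rises alone were kept; they are not a forecast for this trial.

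The table is descriptive, covers the FRC group only and carries no between-group comparison, and SAP Section 2.4.5 plans no testing of safety variables. The primary analysis and the testing sequence are unaffected.

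**What to change.** In SAP Section 2.4.5.7 and Protocol Section 11.4.6.6:

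1. Replace the percentage change in anti-insulin titer with the ratio to baseline, summarised by N, geometric mean, geometric CV, median, minimum and maximum. If a percentage is wanted, show 100 × (geometric mean ratio - 1).
2. State that this change summary is limited to patients who are antibody-positive at baseline.
3. Show separately, by visit, the titers of patients who were negative at baseline and became positive.

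Titers by visit and status conversion stay as planned. The cost is a wording change, one redefined variable and one small extra display, with no new samples or visits. Making the change before database lock avoids an ad hoc choice once titers have been seen.

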2.4.6 Analyses of pharmacokinetic variables

Total plasma concentrations of lixisenatide of patients in the FRC group will be listed and summarized by visit and time window and by anti-lixisenatide antibody status in the PK population, using descriptive statistics by N, geometric mean, coefficient of variation, median, minimum and maximum.

Population PK modeling might be pursued for exploratory purpose by the Pharmacokinetics, Disposition and Metabolism (PKDM) group at Sanofi. Results would be provided in a separate report.

2.5 DATA HANDLING CONVENTIONS

2.5.1 General conventions

The following formulas will be used for computation of parameters.

Renal function formulas

The estimated glomerular filtration rate (GFR) will be calculated by 4 variable MDRD formula using the serum creatinine, race, age, and gender of the patient:

$$\text{GFR (mL/min/1.73 m}^2\text{)} = 175 \times \text{serum creatinine (mg/dL)}^{-1.154} \times \text{age (yr)}^{-0.203} \times 1.212 \text{ [if black]} \times 0.742 \text{ [if female]}$$

Calculation of LDL-C

When TG is lower than or equal to 4.52 mmol/L (400 mg/dL), LDL-C is calculated using the Friedewald equation as:

A) in mmol/L unit, total cholesterol – HDL-C – TG/2.17;

B) in mg/dL unit, total cholesterol – HDL-C – TG/5.

2.5.2 Data handling conventions for secondary efficacy variables

For patients who drop out or are rescued before the end of 26-week randomized treatment, the missing data will be handled by the statistical approach chosen. The missing data will be handled by MMRM approach, or imputed by taking the last available post-baseline measurement as the Week 26 value (see [Section 2.5.4](#)) in ANCOVA-LOCF approach.

For the categorical secondary endpoints, data handling conventions are described in [Section 2.4.4.2](#).

2.5.3 Missing data

For categorical variables, patients with missing data are not included in calculations of percentages unless otherwise specified. When relevant, the number of patients with missing data is presented.

Derived variables will be considered missing if any of the original variables required to calculate them are missing. For example, if either a baseline assessment or an endpoint assessment is missing for a particular patient, then change from baseline at endpoint will be missing. Depending upon the assessment, analyses may not include all patients in the analysis population, because certain patients in the intended population may have missing data.

Incomplete date of first injection

Date of first injection is the first non-missing start date of open-label IMP completed in the eCRF “Investigational medicinal product administration” module.

For patients who are randomized and dispensed a treatment kit but who are lost to follow-up just after Visit 3 (only the treatment kit number is reported in the eCRF “Investigational medicinal product administration” module without any dose information), the date of first injection will be

imputed using the Visit 3 date. When a patient is randomized but not dispensed a treatment kit, the “Investigational medicinal product administration” module should be blank. In this case, the patient will be considered as randomized but not treated, unless the patient’s disposition is not confirmed.

Handling of computation of treatment duration if IMP end of treatment date is missing

For the calculation of the 26-week randomized treatment duration, the date of the last injection of randomized open-label IMP is equal to the date of last administration reported on the eCRF “Treatment Status” page. If this date is missing, the randomized exposure duration should be kept as missing. For the calculation of the treatment duration of whole study for patients participating the extension period, the date of the last injection of IMP is equal to the date of last administration reported on the eCRF “Treatment Status for Extension Phase” page. If this date is missing, the exposure duration should be kept as missing.

In the definition of the 26-week on-treatment period, the date of the last injection of open-label IMP for the patients who do not participate in the extension period is equal to the date of the last administration reported on the eCRF “Treatment Status” page. If the date of last administration reported on the eCRF “Treatment Status” page is missing, for the patients with at least 1 record where the daily dose/weekly dose is greater than zero, the date of the last open-label IMP administration in the “Dose” panel with a daily dose/weekly dose >0 or the date of the last AE reported on the eCRF “Adverse Events” page with “Action Taken with IMP” not ticked “Not Applicable”, whichever is the latest will be used. For the patients who were lost to follow-up after the initial dispensation of IMP, the date of Visit 3/randomization visit will be used.

In the definition of the on-treatment period of the whole study including the 26-week single-arm extension period, the date of last injection of IMP for the patients who participate in extension period is equal to the date of the last administration reported on the eCRF “Treatment Status for Extension Phase” page. If the date of last administration reported on the eCRF “Treatment Status for Extension Phase” page is missing, for the patients with at least 1 record where the daily dose is greater than zero, the date of the last IMP administration in the “Dose” panel with a daily dose >0 or the date of the last AE reported on the eCRF “Adverse Events” page with “Action Taken with IMP” not ticked “Not Applicable”, whichever is the latest will be used. The date of last injection of IMP for the patients who do not participate in extension period is the same as the date of the last injection of open-label IMP in the definition of the 26-week on-treatment period.

Handling of missing data in the calculation of average 7-point SMPG

At least 4 measurements from the 7-points profile are required for calculating the average 7-point SMPG.

Handling of missing data for categorical secondary efficacy endpoints

Please see [Section 2.4.4.2](#).

Handling of medication missing/partial dates

No imputation of medication start/end dates or times will be performed. If a medication date or time is missing or partially missing and it cannot be determined whether it was taken prior or concomitantly, it will be considered a prior, concomitant, and post-treatment medication.

Handling of adverse events with missing or partial date/time of onset

Missing or partial missing AE onset dates and times will be imputed so that if the partial AE onset date/time information does not indicate that the AE started prior to treatment or after the on-treatment period, the AE will be classified as treatment-emergent. No imputation of AE end dates/times will be performed. These data imputations are for categorization purpose only and will not be used in listings. No imputation is planned for date/time of AE resolution.

Handling of adverse events when date and time of first IMP administration is missing

When the date and time of the first IMP is missing, all AEs that occurred after or on the day of randomization and before or on the day of last dose plus 3 days for daily formulation and 9 days for weekly formulation should be considered as TEAEs. The exposure duration should be kept as missing. The last dose intake should be clearly identified in the eCRF and should not be approximated by the last returned package date.

Handling of missing assessment of relationship of adverse events to IMP/NIMP/study procedures

If the assessment of the relationship to IMP/NIMP/study procedures is missing, the relationship to IMP/NIMP/study procedures has to be assumed and the AE considered as such in the frequency tables of possibly related AEs, but no imputation should be done at the data level.

Handling of missing severity/grades of adverse events

If the severity is missing for one of the treatment-emergent occurrences of an AE, the maximal severity on the remaining occurrences will be considered. If the severity is missing for all the occurrences, a “missing” category will be added in summary table.

Handling of potentially clinically significant abnormalities

If a patient has a missing baseline he will be grouped in the category “normal/missing at baseline.”

For PCSAs with 2 conditions, one based on a change from baseline value or a normal range and the other on a threshold value, with the first condition being missing, the PCSA will be based only on the second condition.

For a PCSA defined on a threshold and/or a normal range, this PCSA will be derived using this threshold if the normal range is missing; e.g., for eosinophils the PCSA is >0.5 GIGA/L or $>ULN$ if $ULN \geq 0.5$ GIGA/L. When ULN is missing, the value 0.5 should be used.

Measurements flagged as invalid by the laboratory will not be summarized or taken into account in the computation of PCSA values.

2.5.4 Windows for time points

Nominal post-baseline visits will be used for descriptive statistics and time course plots.

The end of treatment visit is entered as Visit 7000 in the eCRF if a patient prematurely discontinues treatment.

- If Visit 7000 occurs during 26-week randomized treatment period, Visit 7000 will be re-allocated to the next scheduled visit except for the last scheduled on-site visit (Visit 28) at the patient level if the next scheduled visit is an on-site visit but not performed.
- If Visit 7000 occurs during the 26-week single-arm extension period for FRC group, Visit 7000 will be re-allocated to the next scheduled visit except for the last scheduled on-site visit (Visit 35) at the patient level if the next scheduled visit is an on-site visit but not performed. When Visit 7000 is re-allocated to the next scheduled on-site visit at the patient level, a measurement at Visit 7000 for a given parameter will be re-allocated to the same visit only if the re-allocated visit happens to be the next scheduled visit for the given parameter.

When efficacy related parameters are analyzed by MMRM, the post baseline measurements assessed during 26-week randomized treatment period at Visit 7000, Visit 6000 (pre-rescue visit) and Visit 9900 (unscheduled visit) will be re-allocated to the closest scheduled post-baseline visit at the parameter level if the measurement for a given parameter is not available at the scheduled visit. These efficacy related parameters include HbA1c, body weight, 7-point SMPG, FPG. An analysis window will be applied to the re-allocation. In particular, the following rule will be used to determine the analysis window for a scheduled visit for each parameter:

- Lower bound = targeted day of current scheduled visit - integer part of (targeted day of current scheduled visit – targeted day of the preceding scheduled visit)/2;
- Upper bound = targeted day of current scheduled visit + integer part of (targeted day of the next scheduled visit – targeted day of current scheduled visit -1)/2;
- Lower bound for the first scheduled post-baseline visit is always Day 1 (the day of first IMP injection);
- No upper bound is specified for the last scheduled post-baseline visit.

The analysis window for HbA1c is given below for illustration.

Table 3 - Analyses window definition for HbA1c

Scheduled visit post baseline	Targeted study day	Analysis window in study days
Week 8 (Visit 19)	57	1 to 70
Week 12 (Visit 21)	85	71 to 105
Week 18 (Visit 24)	127	106 to 140
Week 22 (Visit 26)	155	141 to 168
Week 26 (Visit 28)	183	169 to 210 (for patients who are eligible to enter the extension period)
		169 to . (for patients who are not eligible to enter the extension period)

Study days are calculated from the day of first IMP injection; the day of first IMP injection is Day 1.

The analysis windows for other parameters analyzed by MMRM can be obtained similarly based on their respective scheduled visits. After applying these time windows, if multiple assessments are associated to the same time point, the closest from the targeted study day will be used. In case of equality, the earliest measurement will be used.

Reference day

The reference day for the calculation of extent of exposure, time to onset, and relative days will be the day of the first injection of open-label IMP, denoted as Day 1.

Baseline definition for efficacy/safety data

For the safety analyses, the baseline for a given parameter is defined as the last available measurement, including unscheduled assessment, assessed prior to the first injection of open-label IMP. For the efficacy analyses, the baseline for a given parameter is defined as the last available measurement, including unscheduled assessments, assessed prior to the first injection of open-label IMP or the last available value on or before the date of randomization if not treated with open-label IMP.

Efficacy endpoints at Week 26

Efficacy endpoints at Week 26 will be assessed using values measured at Visit 28 (Week 26). For ANCOVA-LOCF approach, if a patient discontinues the treatment prematurely, received rescue therapy, or does not have a measurement at Visit 28 for efficacy endpoints, the last non-missing post-baseline value, including measurements from unscheduled visits will be used as the value at Week 26.

Summary statistics by visit for continuous efficacy endpoints

Summary statistics (N, mean, SD, SE, minimum, median, maximum) of continuous efficacy endpoints (observed data and change from baseline) will be provided at scheduled visits as per protocol. Summaries showing data by visit will be presented according to the visit number (or re-allocated visit number) and labeled with the targeted approximate day/week.

Last on-treatment value for laboratory variables and vital signs

The last on-treatment value is the final measurement assessed during the on-treatment period (26-week on-treatment period or the on-treatment period of the whole study) for safety variables, regardless of the introduction of rescue therapy, including measurements at unscheduled visits. A detailed definition of the on-treatment period is provided in [Section 2.1.4](#).

Display of safety data by visit (laboratory variables and vital signs)

Descriptive statistics (N, mean, SD, minimum, median, maximum) of quantitative laboratory variables and vital signs (observed data and change from baseline) during the on-treatment period (26-week on-treatment period or the on-treatment period of the whole study) for all scheduled visits as per protocol will be provided (ie, only including patients having non-missing assessments at a nominal visit). In addition, these summaries will also include a row for the 'last value on-treatment' to describe the last available on-treatment value (see above). Summaries showing data by visit will be presented according to the visit number (or re-allocated visit number) and labeled with the targeted approximate day/week.

As specified in the study protocol, laboratory data from scheduled visits are reported by central laboratories. When both central and local laboratories report values from the same blood sample (ie, sample collected at the same date and time), only measurements from the central laboratory will be included in the analyses. When only local laboratory results are reported and central laboratory results are unavailable, the local results will not be used in the efficacy analyses.

When a patient has more than 1 measurement from the central laboratory for the same laboratory parameter on the same date, the average of the measurements will be used. For the same laboratory parameter, if a patient has more than 1 measurement on different dates for the same scheduled visit, the value closest to the last open-label IMP injection prior to the scheduled visit will be used for the scheduled visit. When the values for the same scheduled visit are equidistant, the last value should be used for the scheduled visit.

Linked adverse events that worsened or became serious

An AE that worsened or became serious will have a separate record in the data from the original event record with a reference identification number that links the new record to the original record. An AE that worsened or became serious will be considered a new recurring AE in the summary of recurrent events or in the summary of events by time intervals.

